1.0 PROTOCOL SUMMARY AND/OR SCHEMA

Study Title	A Safety Study of Avelumab plus SBRT in Malignant Mesothelioma (MPM)
Investigational drug	Avelumab
Study Centers	MSKCC Main Campus and Regional Sites
Study Objectives	To evaluate the efficacy and safety (defined as the incidence of any grade 3+ non-hematologic toxicity) of combining SBRT and avelumab for the treatment of MPM
Study Endpoints	
Primary Endpoint
 
Safety of avelumab + SBRT: rate of grade 3 or higher non- hematologic toxicity (CTCAE v4.0) 
Secondary Endpoint
 
Overall response rate defined by modified RECIST 1.1 for mesotheliomaResponse of irradiated (in-field) and unirradiated (out-of-field) lesions as defined by RECIST 1.1Progression-free and overall survival 
Exploratory Objectives
 
T-cell infiltration both in- and outside the irradiated fieldSerum immune phenotype at baseline and after avelumab + SBRTConcordance of imaging using diffusion-weighted and DCE-MRI, and PET with biopsy sample results
Patient Population	Patients with a histologically/cytologically proven malignant pleural or peritoneal mesothelioma who have received one or more lines of standard treatment.
Number of Patients	27 patients maximum 13 patients will be recruited for Stage 1. If requirements for expansion are met, another 14 patients will be recruited for Stage 2.
Inclusion Criteria (summarized)	
Patient willing and able to provide written informed consent for the trial.Patient age \geq 18 at time of consent.Unresectable or stage IV malignant pleural or peritoneal mesothelioma (MPM).Histological and/or cytological confirmation of MPM.At least one prior therapyAt least one targetable lesion appropriate for palliative SBRT.Karnofsky Performance Score (KPS) \geq 70%Adequate organ function, defined below in Section 6.1

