2.1 OBJECTIVES AND SCIENTIFIC AIMS

- The primary objective of this study is to evaluate the safety of avelumab plus SBRT. This study is designed to include both pleural and peritoneal mesothelioma.
- The secondary objectives are to assess:
 - Overall response rate (ORR) using modified RECIST for mesothelioma treated with SBRT and avelumab.
 - Response of irradiated (in-field) and unirradiated (out-of-field) lesions defined by RECIST 1.1 for extrathoracic disease
 - Progression-free and overall survival
- Exploratory objectives are to evaluate T-cell infiltration and phenotype both in- and outside the irradiated field, serum immune phenotype before and after avelumab plus SBRT, and correlate imaging response (DW/DCE-MRI and PET) with biopsy sample results.

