10.4 Two weeks after Irradiation (+/- 7 days)

1. Repeat biopsy of initially biopsied irradiated lesion and the unirradiated lesion (biopsy to be core needle biopsy up to 4 cores, preferably 18-gauge or larger, specified prior to biopsy, permanently fixed, managed by CSP Correlative Science Program)
2. FDG-PET scan (must be completed prior to biopsy)
3. DW/DCE-MRI with contrast of the lesion to irradiated (must be completed prior to biopsy) as described in Section 8.0 to be completed in the MSKCC Department of Radiation Oncology.

4. Research blood tests

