14.0 BIOSTATISTICS

The primary endpoint, the safety of a combination of avelumab and SBRT, will be defined based on the rate of any grade 3 or higher non-hematologic toxicity within the first 3 months after SBRT (for the rest of the section this will be referred to as AE). A two-stage stopping rule will be used to protect patients' safety. If 3 or more among the first 13 patients develop AEs, then the trial will be stopped and declared unsafe. Otherwise, an additional 14 patients will be enrolled and treated. If, among the total 27 patients, 5 or more patients are observed to have AEs, then the trial will also be declared unsafe. This stopping rule has a power of 80% declaring the true AE rate of 0.1 or lower safe, and a type 1 error rate (alpha) of 5% declaring true AE rate of 0.3 or higher safe.

For secondary endpoints, the overall response and the irradiated lesion and non-irradiated lesion response rates (4 months from start date of the combined therapy) based on RECIST 1.1 response criteria will be summarized by sample proportions and their confidence intervals. PFS and OS will be evaluated by Kaplan-Meier method.

For the exploratory objectives, we will evaluate changes of T-cell infiltration and serum immunophenotype at baseline and after SBRT + immunotherapy both in- and outside the irradiated field. The former is measured as numerical values so we will use Wilcoxon signed-rank test. The latter is categorical so we will tabulate it and employ the marginal homogeneity test. Due to the expected small sample size, results will be interpreted cautiously. The imaging studies using DWI-MRI and DCE-MRI, and FDG-PET will be correlated with biopsy results by McNemar's tests.

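### McNemar's test compares positive rates, so it cannot show whether MRI and PET agree or correlate with biopsy

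*Combined protocol and SAP*

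**What the plan says.** The protocol summary (Section 1.0) lists concordance of diffusion-weighted MRI, DCE-MRI and PET with biopsy as an exploratory objective. Section 2.1 words the same aim as to "correlate imaging response (DW/DCE-MRI and PET) with biopsy sample results". The summary asks about agreement and Section 2.1 about association.

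Section 14.0 gives one method for either: "FDG-PET will be correlated with biopsy results by McNemar's tests", in a sentence that also covers DWI-MRI and DCE-MRI. Nowhere does the document plan kappa, percent agreement, sensitivity, specificity or a correlation coefficient for imaging against biopsy. It gives no rule for calling a scan or a biopsy positive or negative. For T-cell infiltration, the biopsy measure named in the exploratory objectives, Section 14.0 says: "The former is measured as numerical values so we will use Wilcoxon signed-rank test".

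The paired data will exist. Section 8.1 calls for PET, MRI of the lesion to be irradiated, and biopsy of an irradiated and an unirradiated lesion at baseline. Section 10.4 schedules "Repeat biopsy of initially biopsied irradiated lesion and the unirradiated lesion" two weeks after irradiation, with PET and MRI done first.

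**The concern.** McNemar's test is a test of marginal homogeneity. From a paired 2x2 table it takes the two discordant counts (imaging positive only, biopsy positive only) and asks whether they are equal in expectation. The concordant counts do not enter. Whether imaging and biopsy agree lesion by lesion, or rise and fall together, is a different question, and the test's p-value does not answer it.

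Two misreadings are open. A non-significant result could be taken as support for concordance when imaging does no better than chance. A significant result could lead to a useful imaging marker being dismissed, when it tracks biopsy well but over-calls or under-calls in one direction.

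The test also forces both measures into yes/no. If T-cell infiltration is the biopsy readout, that discards information the plan itself treats as numerical. The thresholds would have to be chosen after the plan was written, possibly with the data in view.

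**Working it through.** The plan states no figure for this analysis, so there is none to reproduce. The check is whether the McNemar p-value follows agreement at the trial's size.

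**Inputs.** The number of patients is from Section 1.0: "27 patients maximum 13 patients will be recruited for Stage 1". One pair per patient at one time point therefore gives at most 27 pairs, or 13 if the trial stops after stage 1. The cell counts below are assumptions chosen to illustrate; none is trial data. N = 20 is one further assumed size.

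**Formulas.** Let a = both positive, b = imaging positive only, c = biopsy positive only, d = both negative, and N = a + b + c + d.

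- Exact McNemar: p = min(1, 2 × P(X ≤ min(b, c))), with X binomial (b + c, 0.5). With no discordant pairs, p is taken as 1.
- Observed agreement: po = (a + d)/N.
- Chance agreement: pe = [(a + b)(a + c) + (c + d)(b + d)]/N².
- Cohen's kappa = (po − pe)/(1 − pe).

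**Worked case 1: chance-level agreement, (a, b, c, d) = (7, 6, 7, 7).**

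- po = 14/27 = 0.519.
- pe = (13 × 14 + 14 × 13)/729 = 364/729 = 0.499.
- kappa = (378 − 364)/(729 − 364) = 14/365 = 0.04.
- There are 13 discordant pairs, split 6 to 7, so p = 2 × 0.5 = 1.00.

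**Worked case 2: good agreement with one-sided disagreement, (10, 6, 0, 11).**

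- po = 21/27 = 0.778.
- pe = (16 × 10 + 11 × 17)/729 = 347/729 = 0.476.
- kappa = (567 − 347)/(729 − 347) = 220/382 = 0.58.
- There are 6 discordant pairs, split 6 to 0, so p = 2 × 0.5⁶ = 0.031.

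**All tables.**

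| N | (a, b, c, d) | Agreement | Kappa | McNemar p |
|---|---|---|---|---|
| 27 | (13, 0, 0, 14) | 100% | 1.00 | 1.00 |
| 27 | (11, 3, 3, 10) | 77.8% | 0.55 | 1.00 |
| 27 | (7, 6, 7, 7) | 51.9% | 0.04 | 1.00 |
| 27 | (0, 13, 13, 1) | 3.7% | -0.93 | 1.00 |
| 27 | (10, 6, 0, 11) | 77.8% | 0.58 | 0.031 |
| 20 | (0, 10, 10, 0) | 0% | -1.00 | 1.00 |
| 13 | (6, 0, 0, 7) | 100% | 1.00 | 1.00 |
| 13 | (0, 6, 6, 1) | 7.7% | -0.86 | 1.00 |

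Among the tables of 27, p = 1.00 goes with kappa anywhere from -0.93 to 1.00. The second and fifth rows have the same agreement (21/27) and nearly the same kappa, yet p is 1.00 in one and 0.031 in the other. The only difference that matters to the test is whether the six disagreements split 3 to 3 or 6 to 0. A larger trial would not help: whenever b = c, p is 1.00 at any N, whatever a and d are.

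**What an agreement analysis would report.** For (11, 3, 3, 10), agreement is 77.8% (exact 95% CI 57.7% to 91.4%) and kappa is 0.55 (95% CI 0.24 to 0.87). These are wide intervals, but they answer the question asked.

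**The case against.** The strongest reply concerns weight. This is an exploratory objective with no alpha, power or decision rule attached. The safety rule, the sample size, the response rates and the survival analyses do not depend on it. With at most 27 patients any agreement estimate is imprecise, as the kappa interval above shows. All of that stands, and it limits how serious the point is.

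Section 14.0 also says: "Due to the expected small sample size, results will be interpreted cautiously". That sentence comes before the imaging sentence, and it addresses imprecision. Caution cannot turn a comparison of marginal rates into a measure of agreement. It is fair, though, that the plan sets no rule for reading a non-significant result as concordance, so that misreading is a risk and not a certainty.

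A third reply is that McNemar's test does detect something real in the one-sided table, namely systematic over-calling by imaging, and that the same 2x2 table would let someone compute kappa later. Both are true. The test has a place as a secondary check beside an agreement measure. Here it stands alone, and a measure chosen later is not prespecified.

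Finally, the document never says that the biopsy result in this comparison is T-cell infiltration. A categorical pathology reading may be meant. The point about losing numerical information is therefore conditional, but the lack of any definition or cut-off holds either way.

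**Conclusion.** The concern holds. Used alone, McNemar's test answers neither wording of the objective, and no other analysis of imaging against biopsy is planned. The p-value is 1.00 across practically the whole range of kappa, and it can be significant where agreement is moderate. This is a property of the test and does not depend on the particular tables, which are assumed for illustration.

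The gap lies in the specified statistic and the undefined variables, not in data collection. It should be corrected, because patients have repeat imaging and repeat biopsies that feed this objective. It does not touch the primary safety conclusion.

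**What to change.** Rewrite the imaging sentence in Section 14.0 to do the following.

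- Define the imaging variable for each method, the biopsy variable, the time point (baseline value, post-irradiation value or change), and any cut-off, before the data are examined.
- For binary pairs, report percent agreement and Cohen's kappa with 95% confidence intervals. If biopsy is declared the reference standard, add sensitivity and specificity with intervals.
- For numerical readouts, report Spearman correlation with a 95% confidence interval, for baseline values and for change.
- Where PET supplies both the irradiated and the unirradiated lesion of one patient, analyse the two lesion types separately or bootstrap by patient. Section 10.4 limits MRI to the irradiated lesion, so this arises mainly for PET.
- Name one main measure per imaging method, so that several imprecise estimates are not reported with equal weight.
- If McNemar's test is kept, give it only a secondary role as a check for systematic over-calling or under-calling.

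The cost is a few lines of text and agreement on the definitions. The data, procedures and number of patients stay the same.

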15.1 RESEARCH PARTICIPANT REGISTRATION AND RANDOMIZATION PROCEDURES

15.2 Research Participant Registration

Confirm eligibility as defined in the section entitled Criteria for Patient/Subject Eligibility. Obtain informed consent, by following procedures defined in section entitled Informed Consent Procedures.

During the registration process registering individuals will be required to complete a protocol specific Eligibility Checklist.

The individual signing the Eligibility Checklist is confirming whether or not the participant is eligible to enroll in the study. Study staff are responsible for ensuring that all institutional requirements necessary to enroll a participant to the study have been completed.

All participants must be registered through the Clinical Trials Management System (CTMS) at Memorial Sloan-Kettering Cancer Center. The completed signature page of the written consent/verbal script and a completed Eligibility Checklist and other relevant documents must be uploaded to CTMS. See related Clinical Research Policy and Procedure #401 (Protocol Participant Registration).

15.3 Randomization

Not applicable in this study.

16.1 DAT A M ANAGEMENT ISSUES

A Clinical Research Coordinator (CRC) will be assigned to the study. The responsibilities of the CRC include project compliance, data collection, abstraction and entry, data reporting, regulatory monitoring, problem resolution and prioritization, and coordinate the activities of the protocol study team.

The data collected for this study will be entered into a secured database (Medidata Rave) at Memorial Sloan-Kettering Cancer Center. Source documentation will be available to support the computerized patient record.

16.2 Quality Assurance

Routine data quality reports will be generated to assess missing data and inconsistencies. Accrual rates and extent and accuracy of evaluations and follow-up will be monitored periodically throughout the study period and potential problems will be brought to the attention of the study team for discussion and action. Random-sample data quality and protocol compliance audits may be conducted by the study team, at a minimum of two times per year, or more frequently if indicated.

16.3 Data and Safety Monitoring

The Data and Safety Monitoring Plan utilized for this study must align with the [MSK DSM](#) Plan where applicable.

The Data and Safety Monitoring (DSM) Plans at Memorial Sloan Kettering were approved by the National Cancer Institute in August 2018. The plans address the new policies set forth by the NCI in the document entitled "[Policy of the National Cancer Institute for Data and Safety Monitoring of Clinical Trials.](#)"

There are several different mechanisms by which clinical studies are monitored for data safety and quality. At a departmental/PI level, there exist procedures for quality control by the research team(s). Institutional processes in place for quality assurance include protocol monitoring, compliance and data verification audits, staff education on clinical research QA, and two institutional committees that are responsible for monitoring the activities of our clinical trials programs. The committees: Data and Safety Monitoring Committee (DSMC) for Phase I and II clinical trials, and the Data and Safety Monitoring Board (DSMB) for Phase III clinical trials, report to the Deputy Physician-in-Chief of Clinical Research.

The degree of monitoring required will be determined based on level of risk and documented.

The MSK DSMB monitors phase III trials and the DSMC monitors non-phase III trials. The DSMB/C have oversight over the following trials:

- MSK Investigator-Initiated Trials (IITs; MSK as sponsor)
- External studies where MSK is the data coordinating center

- Low risk studies identified as requiring DSMB/C review

The DSMC will initiate review following the enrollment of the first participant, or by the end of the year one if no accruals, and will continue for the study lifecycle until there are no participants under active therapy and the protocol has closed to accrual. The DSMB will initiate review once the protocol is open to accrual.

17.1 PROTECTION OF HUMAN SUBJECTS

Participation in this trial is voluntary. All patients will be required to sign a statement of informed consent, which must conform to IRB guidelines.

Inclusion of Women and Minorities: Memorial Sloan-Kettering Cancer Center has filed forms HHS 441 (civil rights), HHS (handicapped individual), 639-A (sex discrimination), and 680 (age discrimination); we also take due notice of the NIH policy concerning inclusion of women and minorities in clinical research populations. Patients of all races, both male and female, will be accepted into the protocol. The proposed study population is as described.

Exclusion of Lactating or Pregnant Women: Lactating and pregnant women are also excluded because of unknown effects of immunotherapy on a developing fetus or nursing infant.

Children have been excluded from this study as mesothelioma is an adult cancer. Thus, the relevance of this drug to the pediatric population has not been established.

Benefits: It is possible that this treatment will result in shrinkage of mesothelioma or in a stabilization of an otherwise progressing disease. It is not known, of course, whether these or any other favorable events will occur. It is not known whether this treatment will affect the overall survival of the patients.

Costs: The patient will be responsible for the costs of standard medical care, including, CT scans, all drug administration fees and all hospitalizations, as well as for complications of treatment. Avelumab will be supplied to patients by Pfizer at no cost. Patients will not be responsible for the costs of blood procurement obtained for research purposes, the cost of special testing of any tissue for research purposes, or the cost for obtaining the tumor biopsy for research purposes.

Incentives: No incentives will be offered to patients/subjects for participation in the study.

Alternatives: Patients may be eligible for other investigational studies or focus on palliative care options.

Confidentiality: Every effort will be made to maintain patient confidentiality. Research and hospital records are confidential. Patient's name or any other personally identifying information will not be used in reports or publications resulting from this study. The Food and Drug Administration or other authorized agencies (e.g., qualified monitors) may review patients' records and pathology slides, as required.

17.2 Privacy

MSK's Privacy Office may allow the use and disclosure of protected health information pursuant to a completed and signed Research Authorization form. The use and disclosure of protected health information will be limited to the individuals described in the Research

Authorization form. A Research Authorization form must be completed by the Principal Investigator and approved by the IRB and Privacy Board (IRB/PB).

The consent indicates that individualized, de-identified information collected for the purposes of this study may be shared with other qualified researchers. Only researchers who have received approval from MSK will be allowed to access this information, which will not include protected health information such as the participant's name, except for dates. It is also stated in the Research Authorization that their research data may be shared with others at the time of study publication.

17.3 Serious Adverse Event (SAE) Reporting

An adverse event is considered serious if it results in ANY of the following outcomes:

- Death
- A life-threatening adverse event
- An adverse event that results in inpatient hospitalization or prolongation of existing hospitalization
- A persistent or significant incapacity or substantial disruption of the ability to conduct normal life functions
- A congenital anomaly/birth defect
- Important Medical Events (IME) that may not result in death, be life threatening, or require hospitalization may be considered serious when, based upon medical judgment, they may jeopardize the patient or participant and may require medical or surgical intervention to prevent one of the outcomes listed in this definition
- List any additional events that require SAE reporting (pregnancy, AEs of special interest (AESI), secondary malignancies, etc.)

Note: Hospital admission for a planned procedure/disease treatment is not considered an SAE.

SAE reporting is required as soon as the participant starts investigational treatment/intervention. SAE reporting is required for 30 days after the participant's last investigational treatment/intervention. Any event that occurs after the 30-day period that is unexpected and at least possibly related to protocol treatment must be reported.

Please note: Any SAE that occurs prior to the start of investigational treatment/intervention and is related to a screening test or procedure (e.g., a screening biopsy) must be reported.

All SAEs must be submitted in PIMS. If an SAE requires submission to the HRPP Office per [IRB SOP RR-408 'Reporting of Serious Adverse Events'](#), the SAE report must be submitted within 5 calendar days of the event. All other SAEs must be submitted within 30 calendar days of the event.

The report should contain the following information:

- The date the adverse event occurred
- The adverse event
- The grade of the event
- Relationship of the adverse event to the treatment(s)

- If the AE was expected
- Detailed text that includes the following
 - An explanation of how the AE was handled
 - A description of the participant's condition
 - Indication if the participant remains on the study
- If an amendment will need to be made to the protocol and/or consent form
- If the SAE is an Unanticipated Problem

For IND/IDE protocols: The SAE report should be completed as per above instructions. If appropriate, the report will be forwarded to the FDA by the IND Office.

For multicenter trials where MSK is the data coordinating center, please refer to the MSK Multicenter Trial Addendum. All required SAE reporting to the funders and/or drug suppliers will be completed by MSK only.

17.3.1 SAE Reporting to Study Sponsor / Drug Supplier

The following reportable events must be submitted to Pfizer within 24 hours (or immediately for death or life-threatening events) using the provided Investigator-Initiated Research Serious Adverse Event Form (IIR SAE) with the Pfizer Reportable Events Fax Cover Sheet with each SAE submission.

- Serious Adverse Events
- Exposure during Pregnancy or Breastfeeding (even if not associated with an adverse event)
- Occupational exposure (even if not associated with an adverse event)
- Potential drug-induced liver injury (Hy's Law cases): These events are considered important medical events and should be reported as SAEs.

Detailed guidance on the safety reporting is provided in the Safety Reporting Reference Manual.

Contact information for submission of reportable events to Pfizer:

- Fax: Pfizer U.S. Clinical Trial Department, [contact].
or
- E-mail: [contact], specifying:
 - PROTOCOL:
 - SUBJECT:
 - SITE/PI:
 - SAE/ONSET:

